HE	hand eczema
HECSI	Hand Eczema Severity Index
HIPAA	Health Insurance Portability and Accountability Act
HIV	human immunodeficiency virus
HRT	hormone replacement therapy
IB	Investigator's Brochure
ICD	irritant contact dermatitis
ICD-10	International Classification of Diseases, 10th Revision
ICD-11	International Classification of Diseases, 11th Revision
ICF	informed consent form

Abbreviations and Special Terms	Definition
ICH	International Council for Harmonisation of Technical Requirements for Pharmaceuticals for Human Use
ID	identification
IEC	independent ethics committee
IGA	Investigator's Global Assessment
IGA-CHE	Investigator's Global Assessment-Chronic Hand Eczema
IGA-CHE-TS	Investigator's Global Assessment-Chronic Hand Eczema Treatment Success
IGA-TS	Investigator's Global Assessment–Treatment Success
IL	interleukin
IRB	institutional review board
IRT	interactive response technology
ITT	intent-to-treat
JAK	Janus kinase
MedDRA	Medical Dictionary for Regulatory Activities
NRS	Numerical Rating Scale
OLE	open-label extension
PD	pharmacodynamic(s)
PGIC	Patient Global Impression of Change
QALY	quality-adjusted life-year
QOLHEQ	Quality of Life in Hand Eczema Questionnaire
RNA	ribonucleic acid
RSI	Reference Safety Information
SAE	serious adverse event
SAP	Statistical Analysis Plan
SoA	schedule of activities
SOP	standard operating procedure
SPF	sun protection factor
STAT	signal transducers and activators of transcription
TEAE	treatment-emergent adverse event, AEs reported for the first time or worsening of a pre-existing event after first dose of study treatment
Th	T-helper
TYK	tyrosine kinase
ULN	upper limit of normal
VAS	visual analog scale
WOCBP	woman of childbearing potential
WPAI-ChHD	Work Productivity and Activity Impairment Questionnaire v2.0 in Chronic Hand Dermatitis

1. PROTOCOL SUMMARY

Protocol Title:

A Phase 2, Double-Blind, Randomized, 16-Week, Vehicle-Controlled, Efficacy and Safety Study of Ruxolitinib Cream Followed by an Open-Label Extension Period in Adults With Chronic Hand Eczema

Protocol Number: INCB 18424-226

Objectives and Endpoints:

Table 1 presents the primary and major/key secondary objectives and endpoints.

Table 1: Primary and Secondary Objectives and Endpoints

Objectives	Endpoints		
Primary			
To establish the efficacy of ruxolitinib 1.5% cream BID in participants with CHE.	• IGA-CHE-TS ^a at Week 16.		
Key Secondary			
To further assess the treatment effects of ruxolitinib 1.5% cream BID in participants with CHE.	 ITCH4^b response at Week 16. ITCH4 response at Week 4. ITCH4 response at Week 1 (Day 7). 		

^a IGA-CHE-TS is defined as an IGA-CHE score of 0 or 1 with ≥ 2-grade improvement from baseline.

Overall Design:

Table 2 presents the key study design elements. Further study details are presented after the table.

Table 2: Key Study Design Elements

Study Phase	Phase 2
Clinical Indication	Treatment of adult patients with moderate to severe CHE (IGA-CHE score of 3 or 4).
Population	Male and female participants ≥ 18 years of age with diagnosis of CHE for at least 6 months who have moderate to severe disease activity (IGA-CHE score of 3 or 4) and have been treated with at least 1 prescription CHE therapy.
Number of Participants	Approximately 180 participants will be randomized 1:1 to 1 of 2 treatment groups (ruxolitinib 1.5% cream BID or vehicle cream BID). The participants will be stratified by IGA-CHE score (3 or 4) at baseline and by region (North America or outside of North America).
Study Design	This is a randomized, 16-week, double-blind, vehicle-controlled study with a 16-week open-label treatment extension.

^b ITCH4 response is defined as a ≥ 4-point improvement in CHE-related Itch NRS score from baseline.

Table 2: Key Study Design Elements (Continued)

Estimated Duration of Study Participation	Estimated total duration of participants is up to approximately 40 weeks. • Screening: up to 4 weeks • DBVC period: 16 weeks • OLE period: 16 weeks • Safety follow-up: 30 days
Data Safety Monitoring Board/Data Monitoring Committee	No
Coordinating Principal Investigator	To be determined

Treatment Groups and Duration:

Approximately 180 adult participants with moderate to severe CHE with no history of (within the past 5 years) or current AD will be randomized 1:1 to either ruxolitinib 1.5% cream BID or vehicle cream BID (see Figure 1). During the DBVC period, participants will apply either ruxolitinib 1.5% cream or vehicle cream (both BID) to CHE-affected areas on the hands and wrists (if applicable) for 16 weeks. All areas identified at baseline should continue to be treated through the end of the DBVC period (Week 16) unless the participant meets criteria for stopping study drug (see Section 7.1).

At Week 16, participants with no safety concerns will enter the 16-week OLE period, during which all participants will receive open-label ruxolitinib 1.5% cream. Affected areas will be treated as needed until they clear during the OLE period (see Section 6.1). Participants, investigators, and the sponsor will be blinded to each participant's treatment assignment during the DBVC period. During the OLE period, participants and investigators will remain blinded to the treatment assignment during the DBVC period until after all participants have completed treatment or discontinued and completed the safety follow-up period.

[figure not shown]
Participants who develop additional areas of CHE may treat the additional areas with approval by the investigator as long as there are no safety concerns regarding the application of study drug.

Table 3 presents the SoA. Adherence to the study design requirements, including those specified in the SoA, is essential and required for study conduct.

The COVID-19 global pandemic may present challenges to the normal conduct of this study (including AE and laboratory assessments), requiring the outline of potential mitigation strategies described in Appendix B.

Figure 1 presents the study design schema.

Figure 1: Study Design Schema

^{*}Stratified by baseline IGA-CHE and region.

Table 3: Schedule of Activities

	Days -28 to -1 Screening	Vehicle-Controlled Treatment Day 1 Weeks							en-Label eatment	Safety Follow-Up	
Visit Day (Range)		Day 1 Baseline	2a (± 3 d)	4 (± 3 d)	8	12a	16 ^b /ET1 (± 3 d)	24a (± 3 d)	32/ET2° (± 3 d)	Days 30 ^{a,d} (+ 7 d After Last Application)	Notes
Administrative proced	lures										
Informed consent	X										
Contact IRT	X	X	X	X	X	X	X	X	X	X	
Inclusion/exclusion criteria review	X	X									
Demography and medical history (general and disease specific)	X										
Prior/concomitant medications	X	X	X	X	X	X	X	X	X	X	
Apply study drug in clinic*		X	X	X	X	X	X	X†			*On-site applications will be performed by participants. The application will be under supervision at baseline but not mandated for subsequent visits. †No study drug will be applied at Week 24 if BSA is 0 at the visit.
Distribute reminder card		X	X	X	X	X	X	X	X		
Weigh/dispense study drug		X	X	X	X	X	X	X			
Collect/weigh returned study drug			X	X	X	X	X	X	X		
Assess eDiary and study drug compliance	X*	Χ†	X	X	X	X	X	X	X		*At screening, eDiary will be issued and compliance check is not needed. eDiary for Itch and Skin Pain NRS is to be started at screening, and compliance should be checked starting at baseline. †eDiary for study medication is to be started at baseline, and compliance should be checked starting with the following visit.

Table 3: Schedule of Activities (Continued)

	Days		Vehicl	e-Contro	olled Tre			Tre	n-Label eatment	Safety Follow-Up	
	−28 to −1	Day 1		ı	Week	S		V	Veeks	Days	
Visit Day (Range)	Screening	Baseline	2a (± 3 d)	4 (± 3 d)	8 (± 3 d)	12a (± 3 d)	16 ^b /ET1 (± 3 d)	24a (± 3 d)	32/ET2° (± 3 d)	30 ^{a,d} (+ 7 d After Last Application)	Notes
Safety assessments											
AE assessments	X	X	X	X	X	X	X	X	X	X	If an AE is noted, that body system should be physically examined in a targeted physical examination.
Comprehensive physical examination	X*						Χ†		X		*Including Fitzpatrick skin classification. †Only required for participants not continuing in the OLE period.
Height and body weight	X										
Vital signs	X	X	X	X	X	X	X	X	X	X	
Efficacy assessments											
%BSA	X	X	X	X	X	X	X	X	X	X	The %BSA affected by CHE only (including hands and wrists [if applicable]).
Target lesion		X*			X		X				*At select study sites participating in skin sampling for biomarker collection, a target lesion will be identified at baseline on a hand affected by CHE.
IGA-CHE	X	X	X	X	X	X	X	X	X	X	
HECSI		X	X	X	X	X	X	X	X	X	
Photography		X		X	X		X	X	X		Photographs of the hand and wrist (anterior and posterior) will be taken at all study sites. At select sites, photographs will be marked with the location of the target lesion and nonlesional area at the baseline visit.
CHE-related Itch NRS	X*	Diary is	Diary is completed each evening from screening through Week 32 or ET.						*Average of 7-day (minimum 4/7 days) CHE-related Itch NRS directly prior to Day 1 will be used to determine study eligibility.		

Table 3: Schedule of Activities (Continued)

	Days -28 to -1 Screening	Vehicle-Controlled Treatment						Open-Label Treatment		Safety Follow-Up	
		Day 1 Weeks						V	Veeks	Days	
Visit Day (Range)		Baseline	2a (± 3 d)	4 (± 3 d)	8 (± 3 d)	12a (± 3 d)	16 ^b /ET1 (± 3 d)	24a (± 3 d)	32/ET2° (± 3 d)	30 ^{a,d} (+ 7 d After Last Application)	Notes
Efficacy assessments (continued)					_					•
CHE-related Skin Pain NRS	X	Diary is	comple	ted each	evening f	from scre	ening throu	gh Week	32 or ET.		
DLQI		X	X	X	X	X	X	X	X		
PGIC			X	X	X	X	X	X	X	X	
QOLHEQ		X	X	X	X	X	X	X	X	X	
EQ-5D-5L		X	X	X	X	X	X	X	X		
WPAI-ChHD		X	X	X	X	X	X	X	X	X	
Laboratory assessmen	its										
Chemistry assessments	X	X*			X		X	X	X	X	*Not necessary if screening assessment performed within 14 days of Day 1.
Hematology assessments	X	X*			X		X	X	X	X	
FSH	X*										*Women of nonchildbearing potential only.
Serum pregnancy test	X										WOCBP will have a serum test at
Urine pregnancy test		X		X	X	X	X	X	X	X	screening and a urine test at other visits noted. A positive urine test must be confirmed by a serum test.
HIV serology	X										
PD and translational a	ssessments			•	•	•	•				
							_				

- ^a Visits at Weeks 2, 12, and 24 and safety follow-up can be performed virtually (through telemedicine if applicable) only due to COVID-19–related reasons. No efficacy assessments can be performed virtually (see Appendix B).
- b All Week 16 assessments must be completed before the participant can continue in the OLE. Study drug will not be applied in the clinic at Week 16 for participants not continuing into the OLE period.
- ^c Participants who withdraw early should complete the ET and the safety follow-up visits.
- d For participants in the OLE period who have been in an observation/no treatment cycle with a total IGA-CHE score of 0 (clear) from Week 28 or earlier until Week 32, the Week 32/ET visit will also count as the safety follow-up visit.

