3. OBJECTIVES AND ENDPOINTS

Table 4 presents the objectives and endpoints.

Table 4: Objectives and Endpoints

Objectives	Endpoints					
Primary						
To establish the efficacy of ruxolitinib 1.5% cream BID in participants with CHE.	• IGA-CHE-TS ^a at Week 16.					
Key Secondary						
To further assess the treatment effects of	• ITCH4 ^b response at Week 16.					
ruxolitinib 1.5% cream BID in participants with CHE.	• ITCH4 ^b response at Week 4.					
CIL.	• ITCH4 ^b response at Week 1 (Day 7).					
Secondary						
To further evaluate the efficacy of ruxolitinib	IGA-CHE-TS at each postbaseline visit.					
1.5% cream BID.	• ITCH4 ^b response at Day 3.					
	Change from baseline in CHE-related Itch NRS score at each postbaseline visit.					
	• Time to ≥ 4-point improvement from baseline in CHE-related Itch NRS score.					
	Change from baseline in CHE-related Skin Pain NRS score at each postbaseline visit.					
	• Achieving ≥ 2-point improvement in CHE-related Skin Pain NRS score from baseline to Week 16.					
	• Time to ≥ 2-point improvement from baseline in CHE-related Skin Pain NRS score.					
	Percentage change in HECSI from baseline to Week 16.					
	PGIC score at each postbaseline visit.					
To evaluate the participants' quality of life and other patient-reported outcomes.	• Change from baseline in DLQI score at Weeks 2, 4, 8, 12, 16, 24, and 32.					
	• Change from baseline in EQ-5D-5L score at Weeks 2, 4, 8, 12, 16, 24, and 32.					
	 Change from baseline in QOLHEQ score at Weeks 2, 4, 8, 12, 16, 24, 32, and follow-up. Change from baseline in WPAI-ChHD score at Weeks 2, 4, 8, 12, 16, 24, 32, and follow-up. 					
To evaluate the safety and tolerability of ruxolitinib 1.5% cream BID.	The type, frequency, and severity of AEs as well as changes in vital signs and laboratory data for hematology and serum chemistry.					

Table 4: Objectives and Endpoints (Continued)

Objectives	Endpoints

^a IGA-CHE-TS is defined as an IGA-CHE score of 0 or 1 with ≥ 2-grade improvement from baseline.

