8.2.2. Hand Eczema Severity Index Score

The HECSI divides the hand into 5 areas for assessment (fingertips, fingers [except the tips], palms, back of hands, and wrists). Each of the 5 areas of the hand is assessed separately for erythema, induration/papulation, vesicles, fissuring, scaling, and edema using the following scale: 0, no skin changes; 1, mild disease; 2, moderate disease; and 3, severe disease. To determine the HECSI score, the affected area for each location (total of both hands) is given a score from 0 to 4 (0, 0%; 1, 1%-25%; 2, 26%-50%; 3, 51%-75%; and 4, 76%-100%) based on the extent of clinical symptoms. Finally, the score given for the extent at each location is multiplied by the total sum of the intensity of each clinical feature to calculate the HECSI score (range from 0 to a maximum severity score of 360 points; Held et al 2005). The HECSI score will be assessed at the timepoints indicated in the SoA (see Table 3).

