10.1. Sample Size Determination

Approximately 180 participants will be randomized 1:1 to ruxolitinib 1.5% cream BID or vehicle cream BID.

The sample size is calculated to provide sufficient power (> 80%) to detect a difference between ruxolitinib 1.5% cream BID and vehicle cream BID for the primary and key secondary endpoints. The powers for different endpoints are provided in Table 9. The chi-square test with a 2-sided α of 0.05 is used to calculate the powers.

In addition to providing sufficient power for efficacy variables, the sample size is determined to provide an adequate database for safety evaluations.

Table 9: Powering for Primary and Key Secondary Endpoints

Variables	Response Rates With Ruxolitinib 1.5% Cream BID	Response Rates With Vehicle Cream BID	Power
IGA-CHE-TS at Week 16	26% ^{ab}	10% ^{abc}	80%
ITCH4 at Week 16	40% ^{bc}	18% ^{bc}	90%
ITCH4 at Week 4	35% ^{bc}	12% ^{bc}	95%
ITCH4 on Day 7	30% ^{bc}	10% ^{bc}	92%

^a Based on the results from a Phase 2b study of topical delgocitinib in CHE (Worm 2022).

^b Based on the results from a Phase 3 study of topical delgocitinib in CHE (Bissonnette 2023).

^c Based on the results from the 2 Phase 3 registrational AD studies, INCB 18424-303 and INCB 18424-304.

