10.4.1. Primary Analysis

The key parameters for the primary analysis are provided in Table 11. The primary analysis will be based on the ITT population. The primary alternative hypothesis (superiority of active ruxolitinib 1.5% cream BID compared with vehicle cream) will be tested at a 2-sided $\alpha = 0.05$ level using a Cochran-Mantel-Haenszel test stratified by IGA-CHE score (3 or 4) and region (North America or outside of North America). A summary of IGA-CHE-TS rates will be reported for each treatment group. The p-value and stratum-adjusted IGA-CHE-TS rate difference with 95% CI will be provided (Mantel and Haenszel 1959).

Table 11: Summary of Primary Analysis

Parameter	Definition
Treatment	Ruxolitinib 1.5% cream compared with vehicle cream
Population	ITT population
Variable	IGA-CHE-TS at Week 16: defined as an IGA-CHE score of 0 or 1 with ≥ 2-grade improvement from baseline
Population-level summary	Stratum-adjusted IGA-CHE-TS rate difference with 95% CI

All nonresponders in the DBVC period, participants who discontinue study treatment at any time before the timepoint of interest, and participants who discontinue from the study for any reason will be defined as nonresponders for the nonresponder imputation analysis. Subgroup analysis by baseline characteristic (eg, IGA-CHE, region, or age) will be performed.

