#### 7.3.2. Primary Efficacy Analyses

The key parameters for the primary analysis are provided in Table 4. The primary analysis will be based on the ITT population in the DBVC period. The primary alternative hypothesis (superiority of active ruxolitinib 1.5% cream BID compared with vehicle) will be tested at a 2-sided  $\alpha = 0.05$  level using a CMH test stratified by stratification factors IGA-CHE score (3 or 4) and region (North America or outside of North America). The p-value and overall odds ratio

with 95% CI will be provided. Summary of IGA-CHE-TS rates will be reported for each treatment group. Stratum-adjusted IGA-CHE-TS rate difference (1.5% BID vs vehicle) and 95% CI will be computed using Mantel-Haenszel weights (Mantel and Haenszel 1959).

**Table 4:** Summary of Primary Analysis

Parameter	Definition	
Treatment	Ruxolitinib 1.5% cream compared with vehicle cream	
Population	ITT Population	
Variable	IGA-CHE-TS at Week 16: Defined as an IGA-CHE score of 0 or 1 with ≥ 2 grade improvement from baseline	
Population-level summary	Stratum-adjusted IGA-CHE-TS rate difference with 95% CI	

All nonresponders during the DBVC period, as well as all participants missing Week 16 assessment and who discontinue study treatment at any time before Week 16, or discontinue from the study for any reason, will be defined as nonresponders for the nonresponder imputation analysis.

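### The primary test is valid but uses baseline severity only as IGA-CHE 3 versus 4; adjusting for baseline HECSI, already collected, might add 0 to about 4 points of power

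*Protocol*

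**What the plan says.** Protocol 10.4.1 tests the primary endpoint "using a Cochran-Mantel-Haenszel test stratified by IGA-CHE score (3 or 4) and region (North America or outside of North America". SAP 7.3.2 repeats this: "using a CMH test stratified by stratification factors IGA-CHE score (3 or 4) and region (North America or outside of North America". It adds an odds ratio and a rate difference with Mantel-Haenszel weights. Table 4 of the SAP names the stratum-adjusted rate difference as the population-level summary. The two stratification factors are the randomization factors, set in Protocol Table 2: "The participants will be stratified by IGA-CHE score (3 or 4) at baseline and by region (North America or outside of North America" (likewise Protocol 6.3 and SAP 3.1).

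Inclusion criterion 4 limits screening and baseline IGA-CHE to 3 or 4, so the severity factor has two levels.

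Protocol 8.2.2 defines HECSI as intensity of six signs multiplied by extent, over five hand areas, with a "range from 0 to a maximum severity score of 360 points". Table 3 schedules it at Day 1 for all participants, though not at screening. It already supports a secondary endpoint: "Percentage change in HECSI from baseline to Week 16". Neither document uses baseline HECSI in any analysis of IGA-CHE-TS, and it is not among the subgroup factors in SAP 7.3.3.

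**The concern.** IGA-CHE and HECSI measure different things. SAP Table 3 grades IGA-CHE by the intensity of signs and has no term for extent. HECSI multiplies intensity by extent. On these definitions a grade 3 hand can have one mild and one moderate sign in one area at extent 1, scoring (1 + 2) × 1 = 3. It can also have six moderate signs in five areas at extent 4, scoring 5 × 4 × (6 × 2) = 240. Success requires vesiculation, edema and fissures to be absent, so it is plausible that a hand with more involved area succeeds less often.

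If so, a baseline covariate that costs nothing to collect could sharpen the primary comparison. The primary endpoint is planned at 80% power and stands first in a fixed sequence (Protocol 10.3, SAP 3.2). A gain there also raises the chance that the three ITCH4 tests are reached.

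**Working it through.** **Inputs from the documents.** Sample size: "Approximately 180 participants will be randomized 1:1 to ruxolitinib 1.5% cream BID or vehicle cream BID", so 90 per arm. Rates of 26% and 10% with stated power 80% (Protocol Table 9). Test: "The chi-square test with a 2-sided α of 0.05 is used to calculate the powers".

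**Assumed input.** The prognostic strength of baseline HECSI within an IGA-CHE grade is not in the documents, so a range is used.

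**Step 1: the plan's own figure.** With pooled rate (0.26 + 0.10)/2 = 0.18:

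z = [0.16 × √90 − 1.96 × √(2 × 0.18 × 0.82)] / √(0.26 × 0.74 + 0.10 × 0.90) = (1.518 − 1.065)/0.531 = 0.852

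This gives power of 80.3%, so the stated 80% reproduces. The 95% CI half-width for the rate difference is 1.96 × √(0.2824/90) = 11.0 points.

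**Step 2: analytic gain.** If HECSI explains a share R² of the residual variance, the variance is multiplied by (1 − R²), and 90 per arm acts like 90/(1 − R²).

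| R² | Power | CI half-width (points) | Total N for 80% |
|---|---|---|---|
| 0 | 80.3% | 11.0 | 180 |
| 0.02 | 81.1% | 10.9 | 178 |
| 0.05 | 82.3% | 10.7 | 172 |
| 0.10 | 84.3% | 10.4 | 162 |

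**Step 3: simulated gain, residual CMH.** A logistic model without treatment predicts response from strata and HECSI, and the stratified CMH mean-score test is applied to its residuals. Here r is the within-stratum correlation of baseline HECSI with a latent Week 16 severity whose cut-points give 10% and 26%. Assumed strata: 30% at grade 4, regions split evenly. Entries are power of planned CMH / adjusted CMH.

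| r | 12,000 trials | 4,000 trials | Gain (points) |
|---|---|---|---|
| 0 | 81.9 / 81.7% | 81.8 / 81.5% | −0.2, −0.3 |
| 0.3 | 81.4 / 82.4% | 82.0 / 83.5% | +1.0, +1.5 |
| 0.4 | 82.3 / 84.9% | 82.1 / 84.5% | +2.6, +2.4 |
| 0.5 | 82.3 / 86.6% | 80.5 / 85.3% | +4.3, +4.8 |

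A further simulation at the same rates and sample size gave gains of −0.2, +0.8, +3.2 and +3.6. Type I error of the adjusted test was 4.6% to 5.2% over all three.

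**Step 4: simulated gain, standardized rate difference.** This uses a logistic model with treatment, strata and HECSI (6,000 trials per scenario).

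| Odds ratio per SD of HECSI | Mean R² | CMH / adjusted power | Variance ratio |
|---|---|---|---|
| 1.0 | 0.006 | 81.6 / 81.9% | 1.01 |
| 0.70 | 0.022 | 81.8 / 82.6% | 1.00 |
| 0.50 | 0.063 | 81.3 / 83.8% | 0.95 |
| 0.37 | 0.109 | 80.2 / 85.8% | 0.88 |

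Type I error was 5.3% to 5.5% here, against 4.9% to 5.4% for the CMH. Part of the 5.6-point gain in the last row may therefore reflect a slightly liberal test. Its variance ratio alone (0.8848 unrounded) gives 90/0.8848 = 101.7 effective per arm and z = (1.614 − 1.065)/0.531 = 1.03. That is 84.9% power, a gain of 4.6 points.

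**The case against.** The strongest reply is that this is a choice of method and not a fault. The CMH matches the randomization strata, both documents agree on it, and the stated power reproduces. That stands.

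The benefit also depends on a quantity that nobody can read from the documents. They give the HECSI scale range but no distribution overall or by grade, and no association with IGA-CHE-TS. Most of the signs HECSI scores also enter the IGA-CHE grade, so part of its information is already in the stratum. The top of the assumed range, r = 0.5, is roughly an odds ratio of 0.37 per SD within a grade, which is strong. At weaker values the gain is about 1 point or nil. All of this stands, and it is why the benefit can only be called possible.

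A reader might infer that a chance HECSI imbalance between arms would bias the primary result. It would not: random imbalance within strata is already covered by the test's type I error. Adjustment improves precision and gives a prespecified answer if an imbalance is seen.

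The practical objections also have force. Planned rates imply only 90 × 0.26 + 90 × 0.10 = 32.4 responders, so the model must stay small. HECSI has no screening value to fall back on under the baseline rule in SAP 4.1.3. A p-value from the residual test and an interval from a logistic model can disagree. Protocol 10.4.1 names the CMH too, so a change of primary test is more than SAP wording. These points shape the remedy. They do not remove the case for a supportive analysis.

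**Conclusion.** The point holds as an opportunity for efficiency. The primary CMH is valid but takes baseline severity only as grade 3 or 4, and leaves out a score recorded in all participants that contains extent, which IGA-CHE does not grade. Over assumed correlations of 0 to 0.5 the gain in primary power is about 0 to 4 points (3.6 to 4.8 at the top of the range). The residual test keeps type I error near 5% and loses at most 0.3 points if HECSI is uninformative. The interval narrows little: from 11.0 to 10.7 points at R² = 0.05.

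A reader might go further and infer that power is certainly being lost, or that the primary analysis is deficient. The documents support neither. They contain no measure of HECSI's prognostic value within a grade, and the planned test delivers its stated power under its own assumptions.

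**What to change.** Before the primary database lock, when the sponsor is unblinded, amend SAP 7.3.2 to prespecify a baseline-HECSI-adjusted analysis of IGA-CHE-TS that keeps the rate difference as the summary. There are two acceptable levels:

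- **As the primary test.** Fit IGA-CHE-TS on the randomization strata and baseline HECSI without treatment, apply the stratified CMH mean-score test to the residuals, and keep the unadjusted CMH as a sensitivity analysis. Report the standardized rate difference with 95% CI, and state that the residual test decides if the two disagree.
- **At minimum, as supportive.** Keep the CMH as primary and add the standardized rate difference from a logistic model with treatment, strata and baseline HECSI, naming its variance estimator.

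In either case, state the functional form of HECSI (one term, given about 32 expected responders). Add a treatment-blind rule for missing baseline HECSI, for example imputing the overall baseline mean, so that all ITT participants stay in.

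If the primary test changes, align Protocol 10.4.1 and record the change in SAP 11.1, which now lists none. Protocol Section 10 provides for such an amendment. The supportive option needs only SAP text and one added display.

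No new data or visits are needed. The cost is a slightly less simple analysis, a few lines of code and, for the first option, the document alignment.
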